6.3 OTHER ENDPOINTS

N/A

6.4 COVARIATES

Not applicable as there is no formal hypothesis testing for treatment comparisons.

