effectiveness and safety data in Chinese population, especially large-scale study in real world setting. Therefore, the study is to verify atorvastatin effectiveness and safety in Chinese population, and explore the optimal atorvastatin regimens in high-to-moderate risk for ASCVD.

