#### **8.5. Study Size**

- The NI study is designed to detect the achievement rate of LDL-C value in cardiology patients with atorvastatin therapy in real world setting. The length of follow-up is designed to be 12 weeks.
- In the recently published DYSIS  study, the achievement rate of LDL-C value was about 60% among Chinese patients taking 3 months lipid-lowering therapy. In this NI study, we assumed the achievement rate of LDL-C of 60%, allowable error rate of 1.1%, type I error of 0.05, we calculated a required sample size of 7600 patients. Considering 24% loss to follow-up in real-world setting, the sample size will be 10,000. This sample size will also allow for stratification by sex, age ( $\geq 65$  years), risk stratification (very high risk, high risk, moderate risk and low risk) and baseline disease type (with established CHD, having multiple risk factors, and primary hypercholesterolemia).

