4 HYPOTHESES AND DECISION RULES

4.1 STATISTICAL HYPOTHESES

There are no formal hypotheses specified for the study.

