8.2 STATISTICAL ANALYSES

- **Analysis of Primary (Efficacy) Endpoint**

The primary (efficacy) analysis will be conducted in the FAS analysis population. The proportion of Achievement rate for LDL-C at Week 12 defined as the primary endpoint will be analyzed by calculating a point estimate with confidence interval (CI).

Achievement rate for LDL-C will be summarized overall, within each CVD risk strata, and by dose group within each CVD risk strata. 95% confidence intervals will be estimated.

In addition, percentage of patients who achieve LDL-C therapy target will also be tabulated by sex, age group, dose group and baseline disease type.

- **Secondary Endpoints and Safety Analyses**

Analysis of lipid values and change and percent change in lipid values at week 12 will be performed on the FAS populations. Analysis of the remaining secondary endpoints and safety data will be done on SAS (See [Section 5.2](#)). Data summaries will be presented in tabular and/or and summarized descriptively, where appropriate.

Lipid Parameters

Descriptive summary will be tabulated overall and by dose group within each CVD risk level for percent (%) change from baseline for TC, HDL-C and LDL-C and TG at Week 12.

Study Drug Exposure

Exposure to atorvastatin will be summarized descriptively overall, and by CVD risk level. Duration (days) of study drug taken, daily dose, dose at week 12, and total dose will be summarized. Listings of dosing records with the reason of change dose will also be provided.

Adverse Events

Adverse events will be classified using the medical dictionary for regulatory activities (MedDRA) classification system. The severity of adverse events will be graded according to the principal investigatory judgment and collected in CRF.

Adverse events (such as treatment emergent adverse events; treatment-related adverse events; and serious adverse events, adverse event from early termination to final visit, will be summarized by system organ class (SOC) and preferred term (PT) according to MedDRA terminology.

Adverse events will be summarized overall and by dose group within each CVD risk strata by SOC and preferred term.

Adverse events of special interest ([section 6.2](#)) will be tabulated by preferred term (PT) overall and by dose group within each CVD risk level.

Adverse events leading to discontinuation of trial treatment will be presented overall and by dose group within each CDV risk level.

Dropouts

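### LDL-C goal rates by dose within risk stratum are planned without any account of baseline LDL-C, so a baseline difference between dose groups can bias them in either direction

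*SAP*

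**What the plan says.** SAP 6.4 gives one line on covariates: "Not applicable as there is no formal hypothesis testing for treatment comparisons". SAP 4.1 supplies the premise: "There are no formal hypotheses specified for the study".

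By-dose results are nevertheless a planned display of the primary endpoint. SAP 8.2 states: "Achievement rate for LDL-C will be summarized overall, within each CVD risk strata, and by dose group within each CVD risk strata". Protocol 8.1.2 and SAP 6.1 say the same, with 95% confidence intervals. For lipids, SAP 8.2 adds: "Descriptive summary will be tabulated overall and by dose group within each CVD risk level for percent (%) change from baseline".

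Other provisions that matter here:
- Dose follows the doctor's prescription (protocol 8.2.8, SAP 2.1). SAP 2.1 groups patients by the dose recorded at Week 12, or by the last dose at an unplanned visit if Week 12 is missing.
- Each stratum has one absolute goal, for example LDL-C below 2.59 mmol/L at high risk and below 2.07 at very high risk (protocol 8.2.5, SAP Table 2).
- Baseline lipids are required for entry (protocol 8.2.2). SAP 8.3 tabulates them by dose group and overall, but not by dose within stratum.
- The protocol's rationale (section 6) discusses moderate- versus high-intensity statin in Chinese patients and says the study will "explore the optimal atorvastatin regimens in high-to-moderate risk for ASCVD".

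**The concern.** SAP 6.4 treats adjustment as needed only when something is tested. Confounding does not depend on a test: a descriptive rate with a confidence interval is biased in the same way. Two patients in the same stratum share a goal but not a starting point, and the one who starts higher has further to fall. Risk stratification fixes the goal without equalising the distance to it. If physicians choose dose partly by LDL-C level, or by anything associated with it, the by-dose goal rates mix the effect of dose with the starting level.

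At stake is how the table will be read. The rationale raises the dose-intensity question, and goal rate by dose is the most visible planned result that bears on it. A crude table could show little or no gain at a higher dose that does lower LDL-C more, or could exaggerate the gain.

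**Working it through.** **The plan's own figure.** Protocol 8.5 says "we assumed the achievement rate of LDL-C of 60%, allowable error rate of 1.1%, type I error of 0.05", then "we calculated a required sample size of 7600 patients". With n = z²p(1−p)/d², 1.96² × 0.60 × 0.40 / 0.011² = 7,620, against 7,600 stated. Then 7,600 / (1 − 0.24) = 10,000, as stated. The design is for the precision of one overall proportion. It assumes no dose effect, and nothing below alters it.

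**Inputs for the bias check. All are assumptions.** The documents give no baseline LDL-C distribution, dose response or prescribing pattern. Only the goals, 2.59 and 2.07 mmol/L, come from the documents.
- Lower-dose group: baseline mean 3.2 mmol/L, SD 0.85; mean reduction 38%, SD 12 points.
- Higher-dose group: same SDs; mean reduction 44%; baseline mean shifted by a gap.
- Model: Week 12 LDL-C = baseline × (1 − reduction); goal met if below the stratum's goal.

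Difference in crude goal rate, higher minus lower dose, in percentage points (simulated; repeat runs agree within 0.1):

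| Baseline gap (mmol/L) | Goal 2.59 | Goal 2.07 |
|---|---|---|
| −0.3 | +11.0 | +20.3 |
| 0 | +6.9 | +11.5 |
| +0.3 | +1.3 | +1.7 |
| +0.6 | −5.6 | −8.4 |
| +0.9 | −13.9 | −18.3 |

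**Break-even by hand.** Mean Week 12 LDL-C is equal when the baseline means stand in the ratio (1 − 0.38)/(1 − 0.44) = 0.62/0.56 = 1.107. From 3.2 this is 3.54 mmol/L, a gap of 0.34, which fits the sign change in the table.

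**Sensitivity to the assumed dose response.** With reductions of 35% versus 47%, a 0.6 mmol/L gap cuts the gain from +13.8 to +3.5 points (goal 2.59) and from +22.7 to +4.2 (goal 2.07). The sign changes only by a gap of 0.9 (−3.7 and −5.5). Marked attenuation is robust to this choice; reversal depends on the inputs.

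**Does standardising work?** Second set of assumed inputs: baseline 3.2, SD 0.9; reductions 35% versus 41%, SD 13 points; goal 2.59; true difference about +7.8 points. Standardised over 20 bands of baseline LDL-C:

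| Baseline gap | Crude difference | Standardised |
|---|---|---|
| 0 | +7.8 | +7.8 |
| 0.39 | −1.3 | +7.7 |
| 0.69 | −8.8 | +7.7 |
| 1.05 | −18.2 | +7.4 |

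**Percent change.** In the same runs the between-dose difference in percent change stayed at the true −6.0 points at every gap, because a proportional response does not depend on baseline. With baseline measurement error (SD 0.3) and a positive gap it grew to between −7.2 and −9.1. The pattern was exaggerated, not cancelled.

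**Limit of baseline adjustment.** Week 12 dose can reflect earlier response. In an illustrative run (assumed: about 15% up-titrated after missing goal 2.07), the baseline-standardised difference by Week 12 dose was +3.4 points against a true effect of about +11.6.

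**The case against.** The strongest reply is that the study is descriptive by design. The listed objectives are effectiveness, safety and prescribing patterns (protocol 7.1 and 7.2). Dose exploration is a clause in the rationale, and there are no hypotheses or decision rules. That stands, and it limits how serious the point is. It does not rescue the reason given in SAP 6.4, because the by-dose rates are themselves specified outputs with confidence intervals.

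Second, the plan has partial safeguards. Percent change by dose in the same strata would show greater lowering at a higher dose, and SAP 8.3 would show a baseline lipid gap between dose groups. Both are fair. However, the baseline table is not split by stratum, where the goal rates are reported, and neither table corrects the rates. SAP 8.3 also permits other exploratory analyses, so adjustment is not forbidden; it names no method or variable.

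Third, the direction is not known. Nothing in the documents shows that higher baselines receive higher doses within a stratum, and a gap the other way overstates the gain. This stands, and the claim here is bias in either direction.

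A reader might also infer that the by-dose LDL-C change results can be cancelled or reversed by prescribing higher doses to higher baselines. The plan does not support that: the by-dose lipid table is percent change, which is largely protected.

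**Conclusion.** The point holds for goal rates by dose within risk stratum. SAP 6.4's reason for omitting covariates is not valid for those tables, and a modest baseline gap is enough to matter. Under the assumed inputs a gap of about 0.35 mmol/L removes the higher dose's apparent advantage, 0.6 turns it to about −6 or −8 points, and 0.3 in the other direction raises it to about +11 or +20. These figures show what is possible; they do not estimate what this study will find, since every baseline, response and prescribing input is assumed.

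It would be wrong to infer that the primary result is at risk: the overall achievement rate, its interval and the sample size do not depend on the dose grouping. The change is worth making because the baseline value is already collected, but it is not a condition for the primary analysis to stand.

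**What to change.** Replace the SAP 6.4 statement and extend SAP 8.2 as follows:

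1. Keep the crude goal-rate table by dose within risk stratum.
2. Beside it, show the distribution of baseline LDL-C by dose within each stratum.
3. Add goal rates by dose standardised to the stratum's own baseline LDL-C distribution, also adjusted for age and sex, with 95% confidence intervals. Fit the model separately in each stratum, because the goals differ, and state in advance the minimum cell size below which only crude rates are given.
4. Produce these by Day 1 dose as well as Week 12 dose. Baseline adjustment does not remove bias from titration after a poor response.
5. For this analysis, use every baseline LDL-C report that eligibility accepts. Protocol 8.2.2 allows reports up to 24 hours after the first dose, while SAP 8.2 defines baseline as the last value before treatment and SAP 7 imputes nothing. Patients with only a post-start report would otherwise drop out.
6. Describe all by-dose results as associations.

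An adjusted model for percent change is not needed on these grounds.

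The cost is SAP wording, modest programming, an added table and a model assumption. No new data are needed. Residual confounding by indication remains, and an adjusted table may invite a causal reading, which is why item 6 belongs with it.

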7 HANDLING OF MISSING VALUES

For all endpoints, individual missing data will not be imputed.

8 STATISTICAL METHODOLOGY AND STATISTICAL ANALYSES

8.1 STATISTICAL METHODS

SAS[®] Version 9.4 or later will be used to produce all listings and summary tables.

Summary tables presented by visit will include results from scheduled visits such as Day 1 and Week 12. Unscheduled visits will be listed but not summarized except in the event that an unscheduled result qualifies as a baseline result or other derived endpoint.

- **Analyses for Continuous Data**

Summary statistics for continuous variables/endpoints will be presented with number of observations (n), mean, SD, median, minimum (min), and maximum (max).

- **Analyses for Categorical Data**

Summary statistics for categorical variables/endpoints will be presented with number of observations (n) and percentages.

- **Analyses for Binary endpoints**

Exact methods (Clopper-Pearson Interval) will be used to calculate confidence interval (CI) for the primary (efficacy) endpoint: achievement rate of LDL-C at Week 12.

$$\left[\frac{r}{r + (n - r + 1)F_{1-\alpha/2;2(n-r+1),2r}}, \frac{(r + 1)F_{1-\alpha/2;2(r+1),2(n-r)}}{(n - r) + (r + 1)F_{1-\alpha/2;2(r+1),2(n-r)}} \right]$$

Where r is the proportion of patients who met therapy target level and n is the total number of patients who completed 12-weeks.

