## **7. RESEARCH QUESTION AND OBJECTIVES**

### **7.1. Primary Objective:**

- To evaluate the effectiveness of atorvastatin in Chinese cardiology patients in real world setting.

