#### 8.1.2. Study Endpoint

- **Primary endpoint**

- Achievement rate of LDL-C goals at 12 weeks of therapy of Atorvastatin according to Chinese Guideline on Dyslipidemia Prevention and Treatment in Adult (2007 version). It will be presented with the proportion of patients who achieve the LDL-C goal value. LDL-C target value for the patients with different risk level is defined in the [section 8.2.5](#) per guideline.

$$\text{Achievement Rate} = \frac{\text{No. subjects who achieve LDL-C target value}}{\text{No. subjects who complete 12-week follow up}}$$

- The time of 12-week will be calculated from the day when each patient starts taking atorvastatin. .
- Achievement rate will be summarized overall, within each risk strata, and by dose within each risk strata. 95% confidence intervals will be provided.

- **Secondary endpoint**

- Dosage distribution of Atorvastatin in cardiology patients with different risk stratification at the end of 12-week follow-up
- Safety and tolerability will be evaluated by recording the incidence and severity of adverse events, abnormal physical examination findings, and abnormal laboratory values through 12 weeks of treatment. Especially monitoring the patients who have any the following events:
  - Having muscle symptoms such as myalgia, fatigue, weakness, creatine kinase values 10 times the upper limit of normal, or rhabdomyolysis,
  - Having persistent elevation in alanine aminotransferase, aspartate aminotransferase, or both (defined as two consecutive measurements obtained 4 to 10 days apart that is more than three times the upper limit of the normal range).

- Major adverse cardiovascular events will also be recorded as adverse events, including death, myocardial infarction, stroke, documented unstable angina requiring re-hospitalization, revascularization with either percutaneous coronary intervention or coronary-artery bypass grafting.

Adverse events will be summarized overall and by dose within each risk strata.

- Dropout percentage and reason through 12 weeks of follow-up;

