### **8.9. Strengths and Limitations of the Research Methods**

- Strengths: Large sample size and enrolled patients come from most area of China.
- Limitations: study patient only representatives China cardiology patients, but not a general population.

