2.3 SAMPLE SIZE AND POWER CALCULATIONS

In the recently published DYSIS [1] study, the achievement rate of Low-Density Lipoprotein Cholesterol (LDL-C) value was about 60% among Chinese outpatients taking 3 months lipid-lowering therapy. In this NI study, we assumed the achievement rate of LDL-C of 60%, allowable error rate of 1.1 %, type I error of 0.05, we calculated a required sample size of 7600 patients. Considering 24% loss to follow-up in real-world setting, the sample size will be 10,000.

This sample size will also allow for stratification by sex, age (<65 years vs \geq 65 years), risk stratification (very high risk, high risk, moderate risk and low risk) and baseline disease type (with established CHD, having multiple risk factors, and primary hypercholesterolemia).

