11 APPENDICES

11.1 APPENDIX 1: DATA DERIVATION DETAILS

A1.1 Definition of visit windows

- Baseline (Day 1) is defined after informed consent date signed within one month prior to receive a study drug.
- Study Day = date of assessment – date of first dose of study drug + 1
- Week 12 is defined as Study Day 85 ± 28 days from the Day 1 study drug taken.
- Duration of Study Drug = Date of last dose – date of first dose +1
- End of Study: The Day completion of the study or discontinuation from the study.

A1.2 Demographic and Baseline Variables

- Demographic information : age, gender, height , body weight and BMI
- Medical histories:current or previous medical history, family history of premature atherosclerotic cardiovascular disease (ASCVD) and history of smoking
- Baseline Variables: strata
 - CVD risk level: low, moderate, high, very high, per definition in section 5.4.
 - Liver function tests: ALT, AST, total bilirubin (TBil)
 - Renal function tests: Creatinine (Cr), Blood Urea Nitrogen (BUN), Uric Acid (UA)
 - Serum lipid parameters :LDL-C, HDL-C, TG, Total-C
 - Creatine kinase value (CK)
 - Disease type: established CHD (Coronary Heart Disease), multiple risk factors, and hypercholesterolemia

A1.3 Definition of Derived Variables

Age

- Age = integer of [(informed consent date – date of birth)/ 365.25]
- Age groups: 18 – 64 years old, ≥ 65 years old

Body Mass Index (BMI)

- $BMI = \text{Weight (kg)} / [\text{Height (m)}]^2$

CVD risk level (strata)

The CVD risk level is based on Chinese Guideline on Dyslipidemia Prevention and Treatment in Adult (2007), the cardiovascular disease (CVD) risk stratification. The 10 years CVD risk factors are calculated based on age, sex, total cholesterol, HDL-C, hypertension, smoking history, medical history, and family history.

The CVD risk level for dyslipidemia will be derived.

Reference Normal Laboratory Ranges

The normal laboratory ranges will be defined by local lab facilities.

A2.1 SAS code for exact method

```
proc freq data=Lipitor order=freq;  
  tables LDL-C Goal / binomial (exact) alpha=.05;  
  title 'Exact methods of 95% confidence interval (CI) for rate of LDL-C' ;  
run;
```

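### The 1.1-point precision and the pooled exact interval assume no within-hospital correlation, which the plan neither states nor checks although its target is wider than the roughly 65 hospitals

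*SAP*

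**What the plan says.** The primary result is the proportion of 12-week completers at their LDL-C goal, with a 95% confidence interval. SAP 8.1 fixes the method: "Exact methods (Clopper-Pearson Interval) will be used to calculate confidence interval (CI) for the primary (efficacy) endpoint". SAP Appendix A2.1 implements it in PROC FREQ with "tables LDL-C Goal / binomial (exact) alpha=.05", which contains no site, stratum or cluster term. Site is not among the subgroups in SAP 5.4, and SAP 6.4 names no covariates.

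The interval is wanted at three levels. SAP 8.2 says "Achievement rate for LDL-C will be summarized overall, within each CVD risk strata, and by dose group within each CVD risk strata", and Protocol 8.1.2 asks for the same.

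The study size rests on precision alone. Protocol 8.5 assumes a 60% rate and an "allowable error rate of 1.1%, type I error of 0.05, we calculated a required sample size of 7600 patients", then allows for 24% loss to reach 10,000. The Protocol abstract and SAP 2.3 repeat this. None of these places mentions a design effect.

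Protocol 8.1.1 and 8.2.1 describe one lead hospital and about 64 others, with no account of how they were chosen. The primary objective in Protocol 7.1 is "To evaluate the effectiveness of atorvastatin in Chinese cardiology patients in real world setting". Protocol 8.9 lists as a strength that "enrolled patients come from most area of China". Neither document says whether the hospitals are the whole population of interest or stand for a wider one.

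**The concern.** Patients in one hospital may resemble each other more than patients in different hospitals. The documents give grounds for expecting this. Dose follows the treating doctor's prescription (Protocol 8.2.8, SAP 2.1). The LDL-C target depends on risk level (Protocol 8.2.5), so a site's case mix moves the endpoint directly. Ward inpatients are capped at 20% overall, with no balance by site described (Protocol 8.2.2).

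If results are meant to speak for Chinese cardiology patients, variation between hospitals is part of the uncertainty, and a pooled binomial interval leaves it out. SAP 4.1 states no hypotheses, so the achievement rate and its interval are the main inferential output, and precision is the only basis for the study size. The point estimate is not affected. What is at stake is whether an interval labelled 95%, about 1.1 points either side, deserves that label.

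**Working it through.** **Inputs from the documents.** Rate p = 0.60, error d = 0.011, type I error 0.05, loss 24% (Protocol 8.5, SAP 2.3); about 65 hospitals (Protocol 8.2.1). **Assumed, because the documents do not give them:** the site ICC, the spread of site sizes, and the stratum and cell sizes.

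**Step 1: reproduce the plan's figure.** Under independence, n = 1.96² × p(1 − p) / d² = 1.96² × 0.24 / 0.011² ≈ 7,620, against 7,600 stated (0.3% apart). Then 7,600 / (1 − 0.24) = 10,000. At 7,600 the half-width is 1.96 × √(0.24 / 7,600) = 1.10 points. The Clopper-Pearson interval at 4,560/7,600 is 58.89% to 61.10%, half-width 1.11. So the stated precision is the independent-patients figure, with a design effect of 1.

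**Step 2: overall interval with clustering.** Mean site size m = 7,600 / 65 = 116.9. With equal sites, the design effect is DE = 1 + (m − 1) × ICC. The true half-width is 1.96 × √(0.24 × DE / 7,600). Coverage of the nominal 95% pooled interval is about 2Φ(1.96 / √DE) − 1.

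| Assumed ICC | DE | Half-width (points) | Coverage of pooled 95% CI |
|---|---|---|---|
| 0 | 1.00 | 1.10 | 95% |
| 0.001 | 1.12 | 1.16 | 94% |
| 0.005 | 1.58 | 1.38 | 88% |
| 0.01 | 2.16 | 1.62 | 82% |
| 0.02 | 3.32 | 2.01 | 72% |

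A beta-binomial simulation of the Clopper-Pearson interval itself (65 equal sites, 20,000 runs each) gave 93.7%, 88.5%, 81.8% and 72.6% for the four positive ICCs, in agreement.

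These ICCs imply modest differences between hospitals. The between-hospital SD of the achievement rate is √(0.24 × ICC), about 3.5 points at 0.005 and 4.9 points at 0.01.

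**Step 3: unequal sites.** DE = 1 + ((1 + CV²)m − 1) × ICC. With an assumed CV of 0.5, DE is 1.73, 2.45 and 3.90 at ICC 0.005, 0.01 and 0.02. The half-widths are 1.45, 1.72 and 2.18 points, and coverage is 86%, 79% and 68%.

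**Step 4: would better follow-up absorb it?** With all 10,000 completing, the independent half-width is 1.96 × √(0.24 / 10,000) = 0.960 points. The ICC at which this widens to 1.1 points is ((1.1 / 0.960)² − 1) / (10,000/65 − 1) ≈ 0.002. With 65 hospitals, the half-width cannot fall below 1.96 × √(0.24 × ICC / 65). Above an ICC of about 0.0085, no number of patients per hospital gives 1.1 points.

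**Step 5: risk strata.** For four equal strata of 1,900 (assumed), m = 1,900 / 65 = 29.2. DE is 1.14, 1.28 and 1.56 at ICC 0.005, 0.01 and 0.02, so coverage is about 93%, 92% and 88%. This may be pessimistic, because fixing the risk level removes some of the case-mix difference.

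**The case against.** The strongest reply is that no error has been shown. No ICC is given, so every half-width above 1.10 is conditional on an assumption. If the 65 hospitals are taken as fixed, the pooled interval is not too narrow and may be slightly conservative. A clustered variance treats the hospitals as a random sample, which the documents do not describe, so its coverage is model-based too. The study is also descriptive, with no decision rule that a wider interval would change.

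Much of this stands. The documents show an unstated assumption, not an error of known size, and clustering does not cure a non-random choice of hospitals. But the objective and the claimed national coverage point beyond the participating hospitals, and nothing restricts the conclusion to them. Non-random selection is no reason to leave out between-hospital variance as well. A descriptive study that promises a 95% interval still claims 95% coverage.

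Two stronger readings are tempting and are not supported:

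- A reader might infer that any positive ICC makes the interval too narrow. Clopper-Pearson is slightly conservative, and simulated overall coverage is still about 95% at an ICC of 0.0001.
- A reader might infer that dose-by-risk cells are worst affected, because prescribing could concentrate a dose in a few hospitals. Cell sizes are not given, and small cells have small design effects. A simulated cell of 50 patients in 10 equal sites covers 96.8%, 96.3% and 95.2% at ICC 0.01, 0.02 and 0.05. A cell of 100 in 10 uneven sites falls to 93.7%, 91.6% and 84.6%. The answer turns on layouts that nobody can read from the documents.

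**Conclusion.** The concern holds in conditional form. The 7,600 and the 1.1 points are arithmetically right for their inputs, but they and the planned primary interval rest on independence within hospitals, which is not stated. For the target that the objective names, with the hospitals not treated as fixed, a non-negligible site ICC makes the overall interval too narrow. Over assumed ICCs of 0.001 to 0.02 with equal sites, the half-width is 1.16 to 2.01 points and true coverage about 94% down to 72%; uneven sites make it worse. Risk-stratum intervals suffer less. Dose-by-risk cells cannot be assessed. The size of the effect in this study remains unknown until the ICC is estimated from its data. The change is worth making because the remedy uses data already collected.

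**What to change.** **SAP 8.1, 8.2 and A2.1.** Compute the overall and risk-stratum 95% intervals with site as the cluster, for example in PROC SURVEYFREQ with Clopper-Pearson limits on the effective sample size and degrees of freedom equal to sites minus 1. Report the plain exact interval beside each, together with the observed ICC and design effect. For dose-by-risk cells, keep the plain exact interval and report the number of contributing sites.

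**Study-size text (Protocol abstract and 8.5, SAP 2.3).** State that 1.1% assumes no within-site correlation, and show the half-width over an assumed ICC range such as the table above.

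**Alternative.** If the hospitals are meant as fixed, say so and limit the conclusion to them.

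**Cost.** A few lines of code and some wording, with no extra patients or data. The interval will be wider. If there is no clustering, the simulated mean half-width is 1.16 against 1.11 points overall, and 2.33 against 2.23 per stratum of 1,900. The Protocol asks only for a 95% interval and names no method. However, Protocol 8.7 requires major changes to the primary endpoint's analysis to be reflected in a protocol amendment, so the sponsor should decide whether this change qualifies. The study-size sentence also stands in the Protocol and would need editing there.
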